**FLOW CHART 1 – INTRODUCTION TREATMENT (cont.)**

Trial Periods	Screen	Introduction Study Treatment							FU
	Screen	Cycles 1 - 4 (1 Cycle = 28 days)				EOC4	Cycles 5 & 6**		EOT
Visit	1	Cx V1	Cx V2	Cx V3	Cx V4	C4 V5	Cx V1	Cx V2	
Days (in respective cycle)*	-21 to -1	1	8 ± 1 	15	22 ± 1 	28 ± 2	1	15	
Bone marrow aspiration 	x					X 		X 	X 
Cytogenetics and molecular genetics of MDS 	x					X 			X 
Clinical disease assessment 						x		X 	

TRIAL MEDICATION									
Drug Administration (BI 836858)		x			x			x	x
Best Supportive Care (Phase II Arm B only)		←		x	→				
Eligibility for subsequent cycles of study treatment		X 		X 		X 		X 	X 
End of trial treatment									X 
Other therapies for MDS (Phase II Only)									
Vital Status									X 

EOC4: End of Cycle 4. Patients with clinical benefit, PR or CR after the 4th Cycle and who are tolerating the study treatment may continue on and into the maintenance treatment cycles until PD or other withdrawal criteria are met as noted in [Section 3.3.4.1](#). For patients who have received 8 administrations of BI 836858, this visit will

Proprietary confidential information.

© 2019 Boehringer Ingelheim International GmbH or one or more of its affiliated companies. All rights reserved.

This document may not - in full or in part - be passed on, reproduced, published or otherwise used without prior written permission.

be performed 14 days ( $\pm 2$  days) after the 8th administration of BI 836858. For those patients who received less than 8 administrations, but still in remission, this visit is to be performed 4 months ( $\pm 2$  days) after Cycle 1 Visit 1. Phase II: For patients randomized to BSC, this visit is to be completed 4 months ( $\pm 2$  days) after Cycle 1 Visit 1.

**EOT:** End of Treatment. The EOT visit is to occur 30 days (+7 days) after the last administration of BI 836858. Patients who permanently discontinue study treatment will complete the EOT and complete Follow-up visits. Refer to [Section 3.3.4](#) for treatment discontinuation criteria. After implementation of CTP version 5.0, no further follow-up visits after End of Residual Effect (EoR), unless follow-up is for S(AE) that occurred before EoR period.

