## 4.2 CONCOMITANT THERAPY, RESTRICTIONS, AND RESCUE TREATMENT

### 4.2.1 Rescue medication, emergency procedures, and additional treatment(s)

Rescue medication to reverse the action of BI 836858 is not available. Potential side effects of BI 836858 have to be treated symptomatically. Patients should receive supportive care according to the local guidelines regarding treatment of infusion-related reactions, blood product support, antibiotics, antivirals, analgesics, skin and mouth care, etc. The use of growth factors such as granulocyte colony stimulating factor (G-CSF) will be allowed (other than ESAs), but growth factors should be avoided during the first four administrations (2 cycles) for better assessment of safety and response parameters. G-CSF should not be given prophylactically.

Anti- bacterial and fungal prophylaxis should be given according to local standards or available guidelines.

All concomitant therapies to provide adequate care may be given as clinically necessary. All concomitant treatments will be recorded in the eCRF except for vitamins and nutrient supplements. Trade name, indication and dates of administration of concomitant therapies will be documented. For parenteral nutrition during the trial, the components need not be specified in detail. It should be indicated as 'parenteral nutrition'. If a patient needs anesthesia, it will be sufficient to indicate 'anesthesia' without specifying the details.

Concomitant therapy will be recorded in the eCRF during the screening and treatment period, starting at the date of signature of informed consent, and ending at the EOT-visit. After the EOT-visit, only concomitant therapy indicated for treatment of an adverse event needs to be reported.

After implementation of CTP version 5.0 collection of Concomitant Therapy information only if the indication is treatment of an (S)AE.

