### 4.2.2 Restrictions

#### 4.2.2.1 Restrictions regarding concomitant treatment

Patients must not be receiving any concurrent treatment for MDS while on study. Exceptions will be made for supportive therapies such as transfusions or use of growth factors. The use of colony stimulating factor (G-CSF) will be allowed (other than ESAs), but growth factors should be avoided during the first four administrations (2 cycles) of BI 836858 for better assessment of safety and response parameters. G-CSF should not be given prophylactically.

Iron chelation therapy are permitted to those Phase II patients randomized to BSC only, however these treatments are not allowed for patients receiving BI 836858 in this study.

Short term glucocorticoid medications may be used as clinically indicated to treat infusion-related reactions at any dose. All other indications for steroids have to be discussed and agreed upon between Investigator and Sponsor.

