### 5.1.2.3 Assessment and definition of response criteria

Response to treatment will be evaluated according to the International Working Group (IWG) 2006 criteria ([R13-0369](#)). The evaluation period for transfusion independence and response will last from randomization (for phase II / first administration for phase I) until discontinuation of treatment.

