#### 6.2.3.2 Follow-up

Follow-up visits or telephone calls will be performed after the patient has completed or discontinued treatment according to protocol or is not eligible for further treatment cycles. Follow-up visits or telephone calls will begin 4 weeks after the EOT visit. Follow-up will end in case the patient is lost to follow-up or in case the Investigator and Sponsor agree not to pursue further follow-up visits. In Phase I, Follow-up visits should be performed at 4 week intervals for 6 months. After the 6 month assessment, patients will be considered off trial. In Phase II, Follow-up visits should be performed at 4 week intervals for the first 12 months or earlier if appropriate as determined by the Investigator, and thereafter in 6 month intervals.

Proprietary confidential information.

At the last follow-up visit (Phase I and Phase II), an end of trial assessment will be performed and documented in the eCRF. For follow-up of patients with adverse events which have not recovered at the last planned follow-up visit please refer to [Section 5.2.2.2](#).

The following will be obtained and / or performed:

- AEs since last visit/contact in case they occurred during the residual effect period (30 days after the last trial drug administration) or are considered drug-related (see [Section 5.2.2.1](#))
- Follow-up of AEs in case they were not yet recovered at EOT
- Concomitant therapy indicated for treatment of an AE
- Number of transfusions
- Treatment with any other MDS therapy (report date of treatment and drug)
- Vital status evaluated at each follow-up visit

After implementation of CTP version 5.0, no further follow-up visits after EoR, unless follow-up is for S(AE) that occurred before EoR period.

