5.2.2 Secondary endpoints

The secondary endpoints in Phase I are

- RBC Transfusion Independence (RBC TI)
- Hematologic improvement neutrophils (HI-N)
- Hematologic improvement platelets (HI-P)
- Hematologic improvement erythroid (HI-E)
- Time to HI-E response
- Mean hemoglobin increase ≥ 1.5 g/dL
- Duration of Response (RBC Transfusion Independence, HI-N, HI-P, HI-E or Objective Response)
- Overall Objective Response (OR) [Complete Response (CR), Partial Response (PR), and Hematologic Improvement (HI)]

RBC Transfusion Independence (RBC-TI):

The definition of RBC TI is given in section 5.1.2.3 of the CTP. RBC-TI is evaluated in patients who are transfusion dependent at baseline. Percentages will be calculated using all treated patients, who are transfusion dependent at baseline, as the denominator.

The investigator's assessment as reported on the "Disease Assessment eCRF" will be used for the analysis of this endpoint. No derivation from the "Concomitant Blood Product Therapies eCRF" is planned. Consistency between these two eCRF pages will be reviewed during the trial's Medical Quality Review Meetings (MQRMs).

HI-N, HI-P and HI-E:

HI-N, HI-P and HI-E are defined in section 5.1.2.3 of the CTP. The investigator's assessment as reported on the "Disease Assessment eCRF" will be used for the analysis of these endpoints. No derivation from the "Laboratory eCRF" (or the "Concomitant Blood Product Therapies eCRF") is planned. Consistency between these eCRF pages will be reviewed during the trial's Medical Quality Review Meetings (MQRMs).

Time to HI-E response:

Time to HI-E response is defined only for patients who achieve a HI-E response as follows:

Time to HI-E response [days] = date of first assessment indicating HI-E response – date of first administration of trial medication + 1.

Mean hemoglobin increase ≥ 1.5 g/dL:

The definition of "Mean hemoglobin increase ≥ 1.5 g/dL" is given in CTP section 5.1.2.3.

Duration of Response:

Duration of objective response is defined only for patients who achieve an overall response of CR or mCR or RBC TI.

Duration of response is defined as:

Duration of Response [days] = date of outcome – date of first assessment indicating CR or mCR or RBC TI after first administration of trial medication + 1.

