The censoring rules and dates of outcome (i.e. event or censoring) for Duration of Response under different scenarios are specified in Table 5.2.2:1. The evaluation period for duration of response is until treatment discontinuation (see also section 5.1.2.3 of the CTP).

Table 5.2.2:1 Derivation rules for Duration of Response

| Situation | Outcome (event or censored) | Date of outcome |
|---|------------------------------------|---|
| No relapse, no death | censored | Date of last disease assessment |
| Relapse (no subsequent anti-cancer therapy before relapse) | event | Date of disease assessment of relapse |
| Death without relapse, no subsequent anti-cancer therapy | censored | Date of death |
| Death without relapse, but subsequent anti-cancer therapy prior death | censored | Date of last disease assessment before initiation of subsequent anti-cancer therapy |
| Subsequent anti-cancer therapy before relapse (check interval between start of new medication and relapse) | | |
| Interval ≤ 7 days | Event | Date of disease assessment of relapse |
| Interval > 7 days | Censored | Date of last disease assessment before initiation of subsequent anti-cancer therapy |

Overall Objective Response:

Overall Objective Response is defined as Complete Response (CR), Partial Response (PR), HI-N, HI-P, or HI-E. A patient's "Overall Objective Response" = "Yes" if one of these responses was reported at least once throughout the trial.

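### Duration of Response: the SAP's derivation table does not apply the stated end at treatment discontinuation, and its censoring at death lengthens the listed value

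*SAP*

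**What the plan says.** SAP 5.2.2 defines the duration for patients with CR, mCR or RBC TI. In days it is the date of outcome minus "date of first assessment indicating CR or mCR or RBC TI after first administration of trial medication + 1". On the period it says: "The evaluation period for duration of response is until treatment discontinuation". It cites protocol 5.1.2.3, where the evaluation of transfusion independence and response "will last from randomization (for phase II / first administration for phase I) until discontinuation of treatment".

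Table 5.2.2:1 then sets the outcome dates:
- Alive, no relapse: censored at the last disease assessment.
- Died without relapse, no later anti-cancer therapy: censored at the date of death. Protocol 5.1.2.3 (Duration of Response) has the same rule.
- "Death without relapse, but subsequent anti-cancer therapy prior death": censored at the last disease assessment before that therapy.
- Relapse after later therapy: an event if within 7 days of its start, otherwise censored at the last assessment before it.

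On later therapy, protocol 4.2.2.1 says: "Patients must not be receiving any concurrent treatment for MDS while on study". Both Flow Charts carry the line "Other therapies for MDS (Phase II Only". Protocol 6.2.3.2 lists, with no phase limit, "Treatment with any other MDS therapy (report date of treatment and drug". Protocol 4.2.1 says that after the EOT visit "only concomitant therapy indicated for treatment of an adverse event needs to be reported". SAP 4.2 restricts the analysis to Phase I, and SAP 7.5.2 says durations are listed without summary.

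**The concern.** The sentence and the table give different answers for the same patient, and the SAP does not say which prevails. No row refers to discontinuation, so a programmer working from the table will use deaths and later therapies that fall after the stated end. The two rows for patients without relapse and without later therapy also treat identical assessment data differently, and the difference favours a longer listed response in those who died. The rows that would shorten the value after a change of therapy rely on a start date that Phase I sites are not consistently asked to record. Because no Kaplan-Meier estimate or summary is planned, the listed number is the result that readers see.

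**Working it through.** The plan states no figure to reproduce. The check applies the SAP formula and each table row to one hypothetical patient. All dates below are assumptions, except that EOC4 follows from the schedule.

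**Dates.** Infusions every 14 days put the eighth on Day 1 + 7 × 14 = 99, and EOC4 14 days later on Day 113. Assume the response is first assessed there (RBC TI needs at least 56 transfusion-free days, so this is feasible). Assume the last disease assessment is on treatment on Day 169, with no relapse.

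**Alive or dead.** Duration = outcome date − first response date + 1.
- Alive: 169 − 113 + 1 = 57 days.
- Dead on Day 290, after discontinuation: 290 − 113 + 1 = 178 days.
- Difference: 178 − 57 = 121 = 290 − 169, the gap from last assessment to death.

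The difference always equals that gap, whatever the response date. Months are 12 × days / 365.25.

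| Gap to death (days) | Listed if alive | Listed if dead |
|---|---|---|
| 14 | 57 days (1.9 months) | 71 days (2.3 months) |
| 30 | 57 (1.9) | 87 (2.9) |
| 90 | 57 (1.9) | 147 (4.8) |
| 121 | 57 (1.9) | 178 (5.8) |
| 180 | 57 (1.9) | 237 (7.8) |

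**Where the window ends.** If the last infusion is on Day 169, EOT is due on Day 169 + 30 = 199. An assessment there gives 199 − 113 + 1 = 87 days if it counts as inside the window, and 57 if not. For a patient who stops after the eighth infusion, a window closing on Day 99 would exclude the EOC4 assessment on Day 113. The SAP settles neither case.

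**Later therapy.** Suppose another MDS drug starts on Day 200, then death on Day 290.
- Start recorded: censored at the last assessment before Day 200, so 169 − 113 + 1 = 57 days.
- Start not recorded: the date-of-death row applies, 178 days.

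Since other MDS therapy is barred on study, and protocol 3.3.4.1 requires trial drug to stop once progression or another condition creates an indication for it, these rows normally come into play only after the stated period. The table also has no row for a living patient without relapse who starts later therapy, so assessments made after the switch would count.

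**Scale.** The protocol synopsis gives 21 + 6 = 27 patients in Phase I, and only responders among them have a duration.

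**The case against.** The strongest reply is that censoring at death is the protocol's own prespecified rule, which the SAP follows, and that the longer value is flagged as censored and not as a relapse. That stands: changing it is a departure from the protocol and must be recorded as one. It does not settle whether the window or the table governs.

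Three stronger readings are tempting, and the documents do not support them.

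- A reader might infer that nothing is observed between discontinuation and death. Protocol 6.2.3.2 collects transfusion counts in follow-up, Flow Chart 1 footnote 11 foresees a marrow sample at progression or at the start of other MDS therapy, including in follow-up, and protocol 5.1.2.1 asks for an unscheduled marrow examination when relapse is suspected. What remains is narrower. The SAP takes RBC TI from the investigator's assessment on the Disease Assessment eCRF and plans no derivation from the blood-product page.
- A reader might infer that Phase I does not collect later therapy at all. Section 6.2.3.2 does list it, beside vital status, so before version 5.0 the worst case needs a site to record one item and omit the other. After version 5.0, follow-up visits end at EoR and vital status is no longer mandatory, so late deaths are also less likely to be captured. Deaths do have other routes, through SAE reporting and the Patient Status eCRF, which later therapy lacks. Unreliable is the right word, not absent.
- A reader might infer that the later-therapy rows can never apply inside the window and should be deleted. SAP Table 6.2:1, category D1, provides for additional therapy during the treatment period and excludes nobody for it. Deleting the rows would leave those patients without a rule.

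It is also fair that no test, summary or dose decision uses these durations.

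**Conclusion.** The point holds as an inconsistency that changes listed results. The stated period ends at discontinuation, the table does not, and a death without relapse adds the whole gap since the last assessment to the listed value: 57 against 178 days in the illustration, with a range of 71 to 237 days for gaps of 14 to 180 days. The conflict with the window concerns deaths after discontinuation. A death on treatment is inside it, though the duration still runs past the last assessment. The later-therapy rows add a second, less certain route to the same lengthening, because the Flow Charts and protocol 6.2.3.2 disagree on whether Phase I collects their input.

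The sizes rest on assumed dates, and the documents do not show how many responders died or switched. The impact is modest: a secondary endpoint, listed only, in a Phase I part with 27 entered patients. It is worth correcting because the change is small and gives each patient one reproducible value.

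**What to change.** In SAP 5.2.2:
- State that the discontinuation window governs Table 5.2.2:1. Define discontinuation by a date, and say whether the EOC4 and EOT assessments count as inside.
- Censor every outcome without relapse, death included, at the last disease assessment within that window.
- Keep the later-therapy rows only for therapy started inside the window (on-treatment deviations), alive or dead, using the last assessment before that therapy.
- Record in SAP 4.2 the departure from the death-censoring sentence in protocol 5.1.2.3.

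Do not restrict the listing to patients whose later therapy was recorded. That would select on something that happens after response and would drop responders who never switched.

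The cost is a few lines of SAP text and a change to one listing, if made before database lock. Some listed durations become shorter. A relapse first seen after discontinuation would no longer count as an event, and the SAP should say so.

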### Duration of Response

- Response duration analysis is defined only for patients who achieve CR or mCR or RBC Transfusion Independency and is measured from the first date of achieving a response until the date of relapse. The date of relapse will be the earliest of the dates of the disease assessment (blood sample, bone marrow sample, or clinical assessment) in which the relapse was observed. For patients who die or are lost to follow-up without documented relapse, response duration will be censored, respectively, on the date of death, regardless of cause, or on the date of last disease assessment for the patients who are alive when lost to follow-up.

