### Relapse after CR or PR

- At least 1 of the following:
  - Return to pre-treatment bone marrow blast percentage
  - Decrement of  $\geq 50$  % from maximum remission/response levels in granulocytes or platelets
  - Reduction in Hgb concentration by  $\geq 1.5$  g/dL or transfusion dependence after a period of RBC transfusion independence

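### Relapse is the only duration-of-response event in the SAP, so a loss of RBC TI recorded as PD, or a blast PD below the pre-treatment level, is listed as censored

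*SAP*

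**What the plan says.** SAP 5.2.2 fixes the population: "Duration of objective response is defined only for patients who achieve an overall response of CR or mCR or RBC TI". Table 5.2.2:1 then has six outcome rows. Two are events and both require relapse: "Relapse (no subsequent anti-cancer therapy before relapse", and relapse no more than 7 days after new therapy starts. A living patient without relapse falls under "No relapse, no death" and is censored at the last disease assessment. The other rows censor deaths without relapse, and relapses more than 7 days after new therapy. PD is in none of the six. The section adds: "The evaluation period for duration of response is until treatment discontinuation".

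This follows Protocol 5.1.2.3, where duration is "measured from the first date of achieving a response until the date of relapse". The protocol's relapse criteria carry the heading "Relapse after CR or PR", and the first of them is "Return to pre-treatment bone marrow blast percentage". PD has its own list in the same section. Under SAP 7.5.2, durations of response are listed only.

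**The concern.** Two of the three responses being timed, mCR and RBC TI, have no relapse criterion of their own in 5.1.2.3. The PD list has no such restriction and names the return to transfusion dependence explicitly. An investigator whose patient had RBC TI without CR or PR, and who is transfused again, could reasonably record PD. Nothing in the SAP says that a PD record counts as relapse. For RBC TI itself, SAP 5.2.2 takes the investigator's entry on the disease assessment page and plans no derivation from the transfusion page.

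The case is unlikely to correct itself. Evaluation stops at treatment discontinuation, and Protocol 6.2.2.3 and 6.2.2.5 continue treatment only until PD. The listing would then show a finished response as censored, which reads as still ongoing when last seen. Two patients with the same return to transfusion could be flagged differently because of the label chosen.

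**Working it through.** **1. The two lists side by side (Protocol 5.1.2.3).**

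| Item | Relapse | PD | Does PD imply relapse? |
|---|---|---|---|
| Granulocytes or platelets | fall of at least 50% from best level | the same | yes |
| Hemoglobin | fall of at least 1.5 g/dL | fall of at least 2 g/dL | yes, since 2 > 1.5 |
| Transfusion | dependence after independence | the same | yes |
| Blasts | back to the pre-treatment percentage | rise of at least 50% to above 5, 10 or 20%, by starting band | depends on the reference value |

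By content, the three non-blast PD criteria are also relapse criteria. For these, an ended response is censored only if it is recorded as PD and not as relapse. With k losses of RBC TI recorded that way, the table gives 0 events and k censored instead of k events.

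**2. The blast item.** Let B be the pre-treatment percentage, N the value at response (below 5%) and c the current value. The PD list does not state whether the rise is counted from B or from N. I take the relapse item as c ≥ B.

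- *PD counted from B.* PD needs c ≥ 1.5B, which is at least B, so relapse is always met and there is no gap. For B = 9%, PD needs 1.5 × 9 = 13.5%.
- *PD counted from N.* PD needs c > 5 and c ≥ 1.5N. PD without blast relapse is then c > 5, c ≥ 1.5N and c < B.

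Example on the second reading: 9% to 3% to 6%.

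- mCR: 3% is at most 5%, and (9 − 3)/9 = 67% is at least a 50% decrease.
- PD: (6 − 3)/3 = 100% rise, and 6% is above 5%.
- Relapse by blasts: 6% is below 9%, so not met.

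Windows on the second reading:

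| B | PD without blast relapse |
|---|---|
| 5% or less | none |
| 6% | above 5% to below 6% |
| 9% | above 5% to below 9% (from 1.5 × 4.5 = 6.75% if N = 4.5%) |

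A 0.5%-step grid (B from 0 to 20%, N up to 5%, c up to 30%) agrees. Counted from B, 0 of 10,125 PD states are below the pre-treatment value; counted from N, 4,427 of 19,361 are. These counts show that a gap exists; they are not patient probabilities.

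**3. Effect on one listing line.** The SAP formula is date of outcome − date of first response + 1. Take response on Day 112 and PD on Day 196, at the last disease assessment. Either way the duration is 196 − 112 + 1 = 85 days. Only the flag differs: censored under the table as written, event under the fix.

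**The case against.** The strongest reply is that nearly all PD already meets a relapse criterion, so it is an event by content. That stands, and it defeats a reading the table invites: that any CR, mCR or RBC TI responder who progresses is censored. The documents support this only for an ending recorded as PD without relapse, and for the blast window.

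Other points:

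- **The eCRF is not among the documents.** It may allow both labels, and Protocol 5.2.2.2 speaks of progression and relapse together. This stands: the label problem is a possibility the SAP leaves open, not an observed error.
- **The synopsis mentions relapse after RBC TI and mCR.** True, but it gives no criterion for either and names PD separately.
- **The blast gap needs PD counted from the response value.** This stands; the protocol does not settle the reference.
- **The SAP follows the protocol endpoint.** This stands. It is a design gap, not a deviation.
- **A blast or platelet PD does not end transfusion independence.** This stands, and it rules out simply making every PD an event.

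A reader might also infer that the row "Death without relapse, no subsequent anti-cancer therapy", which censors at the date of death, adds time after PD to the listed duration. The SAP does not say whether its evaluation-period limit overrides that row, so the inference is not established.

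**Conclusion.** The concern holds in a limited form. With relapse as the only event, and no relapse criterion for mCR or RBC TI, some ended responses would be flagged as censored: a loss of RBC TI recorded only as PD, and a blast PD counted from the response value that stays below the pre-treatment percentage. The first rests on PD being recorded without relapse; the second on the reference value and on no other relapse criterion being met. The PD list in the public copy breaks off after the transfusion item, so any further criterion could not be compared.

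The impact is small. Durations are listed without inference, Phase II will not run, and MTD, DLT and yes/no response rates do not change. The ceiling is the 27 Phase I patients (21 + 6); how many are affected is not given. It is still worth correcting, because in so small a listing each line is read individually.

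**What to change.** Make the event row of Table 5.2.2:1 response-specific:

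- **CR and mCR:** relapse or PD, whichever comes first, dated at that disease assessment.
- **RBC TI:** renewed transfusion dependence, whether recorded as relapse or as PD. Other relapse or PD criteria do not end RBC TI.

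Reword the "No relapse, no death" row and the two death rows to refer to the event for the response in question, and keep the 7-day rule. The SAP starts one clock at the first of CR, mCR or RBC TI, so also state which response is being timed when a patient has more than one. Note the change in SAP 4.2 and print the reason for the end of response in the listing.

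The cost is a few table cells, a sentence or two, one line in 4.2 and one listing column, before database lock. It uses relapse and PD as already recorded, and needs no protocol change and no new treatment-stopping rule. One small downside is that the SAP event then differs slightly from the protocol's endpoint at relapse. The fix also cannot recover losses that went unrecorded after protocol version 5.0 made transfusion counts and disease assessments from cycle 5 non-mandatory.

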### Hematologic improvement (HI)

The HI will be evaluated in patients with abnormal pretreatment values defined as follows:

- Erythroid response (HI-E): Patients with a pretreatment hemoglobin  $<11$  g/dL demonstrate erythroid response if their hemoglobin increases by  $\geq 1.5$  g/dL for at least eight weeks, and there is a reduction in the units of red cell transfusions by an absolute number of at least four red cell transfusions per eight weeks compared with the pretreatment transfusion number in the previous eight weeks. Only red cell transfusions given for a hemoglobin  $\leq 9$  g/dL pretreatment will count in the red cell transfusion response evaluation.
- Platelet response (HI-P) — Patients with a pretreatment platelet count  $<100 \times 10^9/L$  demonstrate a platelet response if there is an absolute platelet increase of  $\geq 30 \times 10^9/L$  for patients starting with  $>20 \times 10^9/L$  platelets. For those with an increase from  $10 \times 10^9/L$  to  $>20 \times 10^9/L$  must have an increase of at least 100 percent.
- Neutrophil response (HI-N) — Patients with a pretreatment neutrophil count  $<1 \times 10^9/L$  demonstrate a neutrophil response if they have an at least 100 percent increase and an absolute increase  $>0.5 \times 10^9/L$ .
- Mean hemoglobin increase  $\geq 1.5$  g/dL — Time Frame: Up to approximately 48 weeks. Proportion of subjects achieving hemoglobin (Hgb) increase from baseline  $\geq 1.5$  g/dL over any consecutive 56-day period in absence of Red blood cell (RBC) transfusions.

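### The SAP counts an objective response reported at any point in the trial, whereas the protocol ends response evaluation at treatment discontinuation, and the wider window is not declared

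*SAP*

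**What the plan says.** Protocol 5.1.2.3 fixes one evaluation period for transfusion independence and response, which "will last from randomization (for phase II / first administration for phase I) until discontinuation of treatment".

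SAP 5.2.2 defines Overall Objective Response as CR, PR, HI-N, HI-P or HI-E and scores a patient as a responder "if one of these responses was reported at least once throughout the trial". That sentence has no end date and no rule for treatment stopped or replaced.

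For Duration of Response, the same SAP section does carry the limit: "The evaluation period for duration of response is until treatment discontinuation (see also section 5.1.2.3 of the CTP". Its derivation table also deals with later treatment, for example by censoring at the "Date of last disease assessment before initiation of subsequent anti-cancer therapy". Neither rule is extended to the response rate.

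SAP section 4, which covers changes to the planned analysis, contains a clarification of the DLT endpoint (4.1) and the dropping of Phase II (4.2). It does not mention the response window.

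**The concern.** The window decides who is a responder. If it stays open after BI 836858 is stopped, a blood count or marrow result obtained off drug can turn a non-responder into a responder. Phase I has no control arm against which a misattributed response would show, and the cohorts are small. SAP 7.5.2 tabulates the endpoint by dose cohort and in total, so a single patient is visible in the percentages.

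Two programmers working from the two documents could produce different response rates from the same data, and nothing in the SAP says which is intended.

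**Working it through.** The plan states no figure for this point, so the check is a comparison of texts, a timeline, and the weight of one patient.

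**1. The two windows**

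| | Start | End | Later therapy |
|---|---|---|---|
| Protocol 5.1.2.3, response | first administration (Phase I) | treatment discontinuation | not addressed |
| SAP 5.2.2, Duration of Response | first qualifying assessment | treatment discontinuation | rules given in the table |
| SAP 5.2.2, Overall Objective Response | not stated | end of trial | none |

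The protocol window lies inside the SAP window. Every responder under the protocol rule is therefore a responder under the SAP rule, and the difference can only be extra responders.

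**2. How far the trial runs past the last dose**

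- EOT visit (Protocol 6.2.3.1): 30 days, +7, so day 30 to 37.
- First follow-up contact, 4 weeks after EOT: 30 + 28 = 58 to 37 + 28 = 65.
- Sixth 4-weekly contact (Protocol 6.2.3.2, before version 5.0): 30 + 6 × 28 = 198 to 37 + 6 × 28 = 205.

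**3. Where a post-treatment response could be recorded**

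- *EOT.* Protocol 5.1.2.1 schedules a response marrow at progression or relapse or at EOT, whichever comes first. Section 6.2.3.1 limits the EOT marrow to patients with at least 2 cycles since the end-of-cycle-4 visit, and version 5.0 leaves it to the investigator's discretion. EOT also includes blood counts until version 5.0 makes them discretionary. HI-P as written in 5.1.2.3 has no minimum duration, so one platelet count could meet it. HI-E needs eight weeks (56 days). A rise that began only after the last dose cannot be complete by day 37, but one that began on treatment can be.
- *Unscheduled assessments.* SAP 5.2.2 uses the investigator's report for HI and plans no derivation from laboratory data, so an off-schedule report would count.
- *Follow-up.* The list in 6.2.3.2 includes "Treatment with any other MDS therapy (report date of treatment and drug)" but no disease assessment, and neither Flow Chart schedules one there. The single marrow sample is taken at progression or when other MDS therapy is started, so it cannot show a response to that therapy. Version 5.0 ended visits after the residual effect period, except for (S)AE follow-up.

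**4. Weight of one late responder**

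Input: Protocol synopsis, 21 escalation + 6 expansion = 27 patients.

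- Total: 1/27 = 3.7 points.
- Expansion patients, if tabulated on their own: 1/6 = 16.7 points.
- A dose cohort of 3 (assumed size, the usual minimum in Protocol 3.1): 1/3 = 33.3 points.

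**The case against.** The best defence is that the SAP elaborates the protocol and assumes familiarity with it, so an ever/never rule could be read as operating inside the protocol's evaluation period. This has some force for the haematologic components, since "HI-N, HI-P and HI-E are defined in section 5.1.2.3 of the CTP". It does not settle the composite. CR and PR have no such pointer in the SAP, the composite's own sentence names a different span, and the same section restates the limit for duration alone. Even if the intention was the protocol window, the text needs to say so.

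The second defence is low stakes. The endpoint is secondary, SAP 7.5.2 rules out inference, and the trial ended during Phase I expansion. That is right, and it limits the point to a correction of the response table.

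Three stronger inferences are tempting, and the documents do not support them.

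- *That responses to later therapy inflate the rate by a calculable amount.* Protocol 2.1 gives RBC transfusion independence of 15 to 30% on HMA or lenalidomide, but transfusion independence is not a component of this composite. Under inclusion criterion 1, Phase I patients are refractory to those drugs or not amenable or eligible for them. The documents give no number of patients starting later therapy, and follow-up has no scheduled assessment to detect a response.
- *That the mismatch is what leaves responders without a duration.* Duration is defined only for CR, mCR or RBC transfusion independence, so patients with only PR or HI have none under any window.
- *That the haemoglobin endpoint adds a third conflicting window.* Its "Time Frame: Up to approximately 48 weeks" belongs to a separate endpoint outside the composite.

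It might also be argued that a later-therapy cut-off is redundant because Protocol 4.2.2.1 bars concurrent MDS treatment on study. Section 6.2.3.2 nevertheless foresees other MDS therapy during follow-up, so the cut-off is needed.

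**Conclusion.** The discrepancy is real and lies in current text on both sides. The SAP widens the response window beyond the protocol's without declaring it, and the effect can only raise the response rate. The practical exposure is narrow: mainly EOT and unscheduled assessments, with later therapy possible but unlikely to be captured. The size is 3.7 points per affected patient overall, assuming all 27 patients in the synopsis form the treated set, and more within a dose cohort. The number of affected patients cannot be estimated from the documents. The point merits correction but does not threaten the trial's primary conclusions, which rest on DLTs.

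**What to change.** In SAP 5.2.2, replace the open-ended span in the Overall Objective Response rule with: *from first administration until treatment discontinuation (CTP 5.1.2.3), including the scheduled EOT response assessment, and before any subsequent MDS therapy*. Three details matter.

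- *Name EOT explicitly.* A hard cut at the last dose would discard a planned response marrow. The safety on-treatment period in SAP 6.1 ends 30 days after the last dose, so it would miss an EOT visit on days 31 to 37.
- *Use the same window for RBC transfusion independence, HI and the haemoglobin endpoint.* For haemoglobin, state how it combines with the time frame of about 48 weeks.
- *Do not rely on therapy dates alone.* Flow Chart 1 marks other MDS therapies as Phase II only, whereas Protocol 6.2.3.2 sets no phase limit, so Phase I start dates may be incomplete. The discontinuation limit still works without them.

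List responses first reported after the window separately. If the wider window is intended, declare it in SAP 4.2 with a reason.

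The cost is one sentence, a date filter and a short listing. The descriptive response rate may become slightly less favourable.
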